**6. Analysis Sets**

**6.1 Full Analysis Set (FAS)**

All subjects randomized. Data will be analyzed based on randomized induction period treatment group. **Subject data from site 66164 are not included in the analysis set because the site closed due to noncompliance with the protocol and FDA regulations.**

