In the induction period, 4 dose groups are planned with a placebo group and 3 efavaleukin alfa dose groups: [REDACTED] µg [REDACTED] µg [REDACTED] and [REDACTED] µg [REDACTED]

In the long-term treatment period, subjects randomized to efavaleukin alfa during induction will remain on the same blinded dose throughout the long-term treatment period (both subjects who achieved clinical response at week 12 and those who did not achieve clinical response at week 12). Subjects randomized to placebo who achieved clinical response at week 12 will remain on placebo. Subjects randomized to placebo who did not achieve clinical response at week 12 will receive efavaleukin alfa [REDACTED] µg [REDACTED] in a blinded manner during the long-term treatment period.

For a full description of the investigational product doses, please refer to Section 6.1.1.

Statistical Considerations

The full analysis set will be used for analysis of the primary and secondary efficacy endpoints and will include all subjects randomized. The safety analysis set will include all randomized subjects who received at least 1 dose of investigational product.

Nominal p-values will be reported for the primary and secondary efficacy endpoints, with no adjustment for multiplicity.

The primary estimand will be analyzed using logistic regression to test the difference in clinical remission rates between efavaleukin alfa dose and placebo (Ge et al, 2011). The stratification factors as captured in the interactive response technology (IRT) will be included as covariates. The estimate of the risk difference between each efavaleukin alfa dose and placebo, the corresponding 2-sided 95% Wald confidence interval, and the p-value obtained from the logistic regression model will be provided. Missing primary endpoint data will be imputed using nonresponder imputation.

[REDACTED]

The primary analysis will occur when all subjects have had the opportunity to complete the week 12 visit. All primary and secondary objectives will be evaluated at the primary analysis.

For a full description of statistical analysis methods, please refer to Section 9.

[figure not shown]
Statistical Hypotheses

The primary hypothesis is that at least 1 efavaleukin alfa dose will have greater efficacy compared to placebo as measured by clinical remission rates at week 12 in subjects with moderately to severely active UC.

Sponsor Name: Amgen Inc.

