9.3 Populations for Analysis

Population	Description
Full Analysis Set	All subjects randomized, analyzed by planned treatment group
Safety Analysis Set	All subjects randomized and received at least 1 dose of investigational product, analyzed by actual treatment group

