**6.2 Safety Analysis Set**

Subjects randomized and received at least 1 dose of investigational product. Data will be analyzed according to actual treatment received. **Subject data from site 66164 are not included in the analysis set because the site closed due to noncompliance with the protocol and FDA regulations.**

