#### 6.5 Anti-drug Antibody Analysis Set

Anti-drug Antibody Analysis Set is defined as the subset of subjects in the Safety Analysis Set who had at least 1 evaluable anti-drug antibody test. Immunogenicity data will be analyzed according to the actual treatment received. **Subject data from site 66164 are not included in the analysis set because the site closed due to noncompliance with the protocol and FDA regulations.**

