### **11.        Changes From Protocol-specified Analyses**

- The third interim analysis conducted for the study in August 2024 revealed that the study met futility criteria, leading to its termination. As a result of this decision, select exploratory endpoints originally included in the Statistical Analysis Plan (SAP) are being removed. These endpoints will not be discarded entirely; instead, they will be documented in a Supplemental Statistical Analysis Plan (SSAP) and will not be documented in CSR.
- Subject data from site 66164 are not included in the analysis set because the site closed due to noncompliance with the protocol and FDA regulations. The following listings for the affected subjects will be generated separately:
  - Adverse Events
  - Concomitant Medications
  - Laboratory Data

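### Site 66164 is removed from every final analysis set, so no final efficacy analysis or safety table covers the all-randomized and all-dosed populations of Protocol 9.3

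*SAP*

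**What the plan says.** Protocol 9.3 defines the FAS as "All subjects randomized, analyzed by planned treatment group" and the Safety Analysis Set as "All subjects randomized and received at least 1 dose of investigational product, analyzed by actual treatment group". The protocol synopsis says that the FAS, used for the primary and secondary efficacy endpoints, "will include all subjects randomized". None of these texts excludes a site.

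SAP 6.1 also opens by defining the FAS as everyone randomized, and SAP 6.2 opens with "Subjects randomized and received at least 1 dose of investigational product". Each then adds the same restriction: "Subject data from site 66164 are not included in the analysis set because the site closed due to noncompliance". SAP 6.4 (long-term efficacy) and 6.5 (anti-drug antibody: "Subject data from site 66164 are not included in the analysis set") repeat it. SAP 6.3 (interim sets) does not.

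SAP 11 lists the exclusion among the changes from the protocol and gives the reason. It then states: "The following listings for the affected subjects will be generated separately", naming adverse events, concomitant medications and laboratory data.

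**The concern.** The definitions in SAP 6.1 and 6.2 no longer describe the sets they define. A reader who sees FAS or Safety Analysis Set in a table will take it to mean all randomized or all dosed subjects, as the protocol says, and it will mean neither.

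Safety is the more important half. Doubtful data quality is a reason to set aside a site's efficacy scores. It is a weaker reason to leave people who received the product out of the denominators and incidence tables. Their events would appear only subject by subject, outside every summary by arm.

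For efficacy, the question is whether the primary result depends on the exclusion. That can be answered only by a run that includes the site, and none is planned.

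**Working it through.** **1. The sets compared**

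| Set | Protocol 9.3 | SAP |
|---|---|---|
| Full Analysis Set | all randomized | all randomized, less site 66164 (6.1) |
| Safety Analysis Set | all randomized and dosed | the same, less site 66164 (6.2) |
| Long-term efficacy | not defined | site 66164 removed (6.4) |
| Anti-drug antibody | not defined | site 66164 removed (6.5) |
| Interim sets | not defined | no exclusion stated (6.3) |

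**2. Does any planned output bring the site back?**

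- SAP 9.5.2 has one additional analysis of the primary endpoint. It changes the intercurrent-event strategy and names no other population.
- SAP 4.2 plans no subgroup analysis.
- Protocol 9.4.2.3 places all safety analyses on the Safety Analysis Set. The adverse event and exposure tables of SAP 9.6.1 and 9.6.7 therefore omit the site.
- SAP 9.2 (subject accountability) names no analysis set, so it is unclear whether the site is counted there.
- SAP 11 gives listings only, with none for efficacy or exposure.

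No planned final efficacy analysis or safety table includes these subjects.

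**3. Scale (illustration only)**

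The planned allocation is consistent: 4 × 60 = 240. The power statement is redacted, so it cannot be reproduced, and neither document gives the site's size. I assume k site subjects per arm (4k in total) for k = 1, 2, 3, 5, which is 4/240 = 1.7% to 20/240 = 8.3% of the trial. The true number could be smaller, and it could be uneven across arms.

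*One remission:* 1/60 = 1.7 points.

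*Precision.* The illustrative rates are those of two induction trials of another drug cited in Protocol 2.2.1.1, not this trial's design rates. At 60 against 55 per arm (k = 5), power is 38.0% against 35.3% for 8.2% vs 18.5%, and 66.0% against 62.2% for 3.6% vs 16.6%. The loss is small.

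*Risk difference.* Assume 11 remitters on a dose and 5 on placebo among the retained subjects, with an unadjusted Wald test.
- Site excluded: RD = (11 − 5)/(60 − k).
- Site restored: RD runs from (6 − k)/60, if the site's placebo subjects all remit and its dose subjects do not, to (6 + k)/60 for the reverse.

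| k | Excluded: RD (p) | Restored, lowest: RD (p) | Restored, highest: RD (p) |
|---|---|---|---|
| 1 | 10.2 (0.103) | 8.3 (0.187) | 11.7 (0.063) |
| 2 | 10.3 (0.102) | 6.7 (0.304) | 13.3 (0.037) |
| 3 | 10.5 (0.102) | 5.0 (0.452) | 15.0 (0.021) |
| 5 | 10.9 (0.101) | 1.7 (0.81) | 18.3 (0.006) |

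With the site's subjects restored as nonresponders, RD = 6/60 = 10.0 points (p = 0.103) for every k.

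The ends of these ranges are extremes. At k = 2 only one outcome takes p below 0.05: both dose subjects remit and neither placebo subject does. At 18.5% and 8.2% its probability is 0.185² × 0.918² = 2.9%.

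*Yardstick.* The 95% Wald half-width at 60 per arm is 1.96 × √[(p₁(1 − p₁) + p₀(1 − p₀))/60]. It is 12.0 points for 18.5% vs 8.2% and 10.5 points for 16.6% vs 3.6%. One remission is therefore about one-seventh to one-sixth of the half-width.

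*Safety.* The 95% upper bound for an event not seen in n subjects is 1 − 0.05^(1/n). For 180 efavaleukin subjects it is 1.65%. With 15 dropped (165, k = 5) it is 1.80%.

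**The case against.** The case for leaving the plan alone has real weight.

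- **The change is declared.** SAP 11 names it and gives the reason, and Protocol 9.4 allows the SAP to be finalized up to database lock. Nothing is concealed. This stands, but disclosure does not show whether the result depends on the exclusion.
- **Removing a whole site is not the same as removing subjects by outcome or adherence.** If the decision ignored arm and outcome, the remaining subjects are still compared as randomized. A reader might infer that the primary comparison is biased because randomization was not stratified by site. That does not follow: uneven removal across arms means chance imbalance and some loss of precision, not bias. This stands.
- **Timing.** SAP v3.0 is dated 19 February 2025, after the August 2024 interim analysis met futility. A reader might infer that the exclusion was chosen with results in view. The documents do not say when the site closed, when the exclusion was decided or whether the decision was blinded, so they do not support that inference.
- **The safety data are not lost.** Adverse events will be listed, and Protocol 8.4.4.1.2 requires serious events to be reported to the sponsor. This stands in part: tabulation, denominators and exposure are still missing.
- **Little turns on a p-value here.** P-values are nominal without multiplicity adjustment, and the trial was stopped. This limits the efficacy half. It does not touch the safety tables or the mismatch between the sets and their definitions.

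**Conclusion.** The point holds as a reporting gap with an inexpensive remedy. The final FAS and Safety Analysis Set are not the populations in Protocol 9.3, and no planned final efficacy analysis or safety table restores them. The safety tables are the strongest part. The efficacy sensitivity analysis is reasonable but less pressing in a terminated phase 2 study.

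The size is unknown. The calculations rest on an assumed site of 4 to 20 subjects spread evenly over the arms, assumed remitter counts and another drug's remission rates. Within that range the loss of precision is small and counting the site as nonresponders barely moves the estimate. Observed outcomes could move it by k/60 in either direction (1.7 to 8.3 points) around 10.0, with the ends unlikely.

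Two stronger readings go beyond the documents. One is that the efficacy comparison is invalid or biased, which nothing in them shows. The other is that no analysis at all included these subjects: SAP 6.3 states no exclusion, so the interim analyses may have included them. Whether the stopping decision rested on a different population is left open.

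**What to change.** 1. **Safety.** Keep the site's dosed subjects in the Safety Analysis Set, or show the adverse event, serious adverse event, death and exposure summaries with and without the site.
2. **Efficacy.** Add a sensitivity analysis of week 12 clinical remission on all randomized subjects, with the site's subjects once as observed and once as nonresponders. The reduced set may stay the main one.
3. **Reporting.** State the number of subjects excluded per arm. If the reduced set stays the main set, rename it (for example, modified FAS) so that its name and definition agree. One sentence in SAP 6.3 should say whether the interim sets included the site.

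The cost is a few reruns of existing tables. The downside is that some data of doubtful quality enter supportive tables, which a footnote can flag. If the efficacy scores prove unusable, the nonresponder version can still be run, because it needs only arm and stratification factors.

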**6.2 Safety Analysis Set**

Subjects randomized and received at least 1 dose of investigational product. Data will be analyzed according to actual treatment received. **Subject data from site 66164 are not included in the analysis set because the site closed due to noncompliance with the protocol and FDA regulations.**

**6.3 Interim Analysis Sets**

The interim analysis sets will include all subjects enrolled and had the opportunity to complete the week 12 visit by the data cutoff date for the respective interim analysis.

**6.4 Long-term Treatment Period Efficacy Analysis Set**

The long-term treatment period efficacy analysis set is defined as all subjects who received at least one dose of any efavaleukin alfa dose in the induction period plus subjects who were randomized to placebo in the induction period and received at least one dose of IP in the long-term treatment period. Data will be analyzed according to randomized treatment in the induction period. The exception will be subjects randomized to placebo in the induction period who will be further categorized into the treatment assigned via IRT in the long-term treatment period (i.e. assigned placebo in long-term treatment period and assigned efavaleukin alfa in long-term treatment period). **Subject**

data from site 66164 are not included in the analysis set because the site closed due to noncompliance with the protocol and FDA regulations.

[figure not shown]
#### 6.5 Anti-drug Antibody Analysis Set

Anti-drug Antibody Analysis Set is defined as the subset of subjects in the Safety Analysis Set who had at least 1 evaluable anti-drug antibody test. Immunogenicity data will be analyzed according to the actual treatment received. **Subject data from site 66164 are not included in the analysis set because the site closed due to noncompliance with the protocol and FDA regulations.**

### 7. Planned Analyses

#### 7.1 Interim Analysis and Early Stopping Guidelines

Interim analyses will be conducted to assess for futility. Interim analyses will be conducted by an external Independent Biostatistics Group and results evaluated by an independent DMC.

where  $d \in \{ \text{[REDACTED] } \mu\text{g}, \text{[REDACTED] } \mu\text{g}, \text{[REDACTED] } \mu\text{g} \}$ .

In the case where prespecified decision rules are met at a planned interim analysis, a Data Access Plan (DAP) Team will be invoked. The DAP Team is comprised of a small team of senior executives internal to Amgen but external to the study team. To facilitate

final decision making, the DAP Team may evaluate unblinded results. Further details will be described in a Data Access Plan.

The study team, investigators, and subjects will remain blinded to the results of the interim analyses.

## **7.2 Primary Analysis**

The primary analysis will occur after all subjects have completed the week 12 visit or have early terminated. The primary objective of the primary analysis is to evaluate the effect of efavaleukin alfa on induction of clinical remission. All secondary objectives and induction period exploratory objectives will also be evaluated at the time of the primary analysis.

Data will be subject to ongoing checks for integrity, completeness and accuracy in accordance with the Data Management Plan with the expectation that outstanding data issues are resolved ahead of the lock to the extent possible. The data supporting the primary analysis will be locked to prevent further changes.

## **7.3 Final Analysis**

Final analysis activities will commence upon achieving the EOS, defined as the date when the last subject across all sites is assessed or receives an intervention for evaluation in the study (i.e. Last subject last visit), including safety follow-up. The final analysis will include analysis of efficacy and safety data collected during the exploratory long-term treatment period.

Data will be subject to ongoing checks for integrity, completeness and accuracy in accordance with the Data Management Plan with the expectation that all outstanding data issues are resolved ahead of the final lock.

## **8. Data Screening and Acceptance**

### **8.1 General Principles**

The objective of the data screening is to assess the quantity, quality, and statistical characteristics of the data relative to the requirements of the planned analyses.

### **8.2 Data Handling and Electronic Transfer of Data**

The Amgen Global Study Operations-Data Management (GSO-DM) department will provide all data to be used in the planned analyses. This study will use the RAVE database. All laboratory values from the central laboratory will be transferred to GSO-DM. All Patient Reported Outcome (PRO) data, endoscopy results (including Mayo endoscopic subscore and Geboes score from the mucosal biopsy), and individual Mayo

subscores from the central vendors will be transferred to GSO-DM. All other data will be captured on the eCRF.

### **8.3 Handling of Missing and Incomplete Data**

Subjects may have missing specific data points for a variety of reasons. In general, data may be missing due to a subject's early withdrawal from study, a missed visit, or non-evaluability of a specific clinical measurement at its planned clinical visit. Missing data will not be imputed, except for the data points described below.

Non-responder imputation will be used to impute missing data for the following binary endpoints: clinical remission, clinical response, endoscopic remission, symptomatic remission, combined endoscopic and histologic remission, corticosteroid-free clinical remission.

If a subject has missing data for any of these endpoints, (including missing one or more subscores contributing to the endpoint) at any scheduled visit, the subject will be considered as not meeting the endpoint for that specific visit.

Missing data for the following continuous endpoints will be imputed with worst case imputation: change in Geboes score, total Mayo score, partial Mayo score, and individual Mayo subscores.

**Observed subscores will be used in the calculation of total and partial mayo score, where available. If one or more individual subscores is missing at a given post-baseline timepoint, the missing subscore will be imputed using the worst (highest) observed score across all available baseline and post-baseline visits up to week 12. The total/partial mayo score will be calculated using the imputed subscores, along with observed subscores, if available for that visit.**

Laboratory measurements that are below the lower quantification limits will be considered equal to the lower limit of quantification for all analyses unless explicitly noted otherwise.

Incomplete UC diagnosis date will be imputed as follows:

- If day is missing but month and year are present, impute to the last day of the month
- If day and month are missing and year is present, impute to the 31st December of that year

Missing and incomplete dates of medical history, procedures, AE, concomitant medication and hospitalization dates will be imputed as outlined in [Appendix C](#).

#### **8.4 Detection of Bias**

Important protocol deviations and early withdrawal from treatment and from study may bias the results of the study. The incidence of these factors will be assessed and reason for early withdrawals will be tabulated.

#### **8.5 Outliers**

Scatter plots will be examined to identify potential outliers in any of the continuous variables and frequencies of the categorical data will be examined to identify questionable values. The validity of any questionable values will be verified, and observations found to be due to data entry errors will be queried. Potential outliers that are not due to data entry error will be included in the analysis.

#### **8.6 Distributional Characteristics**

Not applicable for this study.

#### **8.7 Validation of Statistical Analyses**

Programs will be developed and maintained and output will be verified in accordance with current risk-based quality control procedures.

Tables, figures, and listings will be produced with validated standard macro programs where standard macros can produce the specified outputs.

The production environment for statistical analyses consists of Amgen-supported versions of statistical analysis software; for example, the SAS System version 9.4 or later.

### **9. Statistical Methods of Analysis**

#### **9.1 General Considerations**

All categorical variables will be summarized using the number and percent of subjects falling into each category and all continuous variables will be summarized using mean, standard deviation (SD), median, first quartile (Q1), third quartile (Q3), minimum, maximum, and number of subjects with observations.

Nominal p-values will be reported for the primary, secondary, and select exploratory efficacy endpoints, with no adjustment for multiplicity.

Safety endpoints will be summarized descriptively, including treatment-emergent adverse events and serious adverse events in the induction period, clinically significant changes in laboratory values and vital signs, and incidence of antidrug antibodies.

Exposure-adjusted treatment-emergent adverse events and serious adverse events will be summarized for the overall study period.

### **9.2 Subject Accountability**

The number and percent of subjects who were randomized, received investigational product in the induction period, discontinued investigational product in the induction period (including reasons for discontinuing), completed investigational product in the induction period, and completed the induction period will be summarized overall and by randomized treatment group.

The number and percent of subjects who completed investigational product for the overall study, discontinued investigational product at any time during the study (including reasons for discontinuing), and overall study completion (defined as completed study on the eCRF) will be summarized overall, by randomized treatment group, and week 12 response status (subjects randomized to placebo only).

Summary of subjects who discontinue investigational product/study due to COVID-19 control measures will be included.

Key study dates for the first subject enrolled, last subject enrolled, last subject's end of investigational product, and last subject's EOS will be presented.

### **9.3 Important Protocol Deviations**

Important Protocol Deviations (IPDs) categories are defined by the study team before the first subject's initial visit and updated during the IPD reviews throughout the study prior to final database lock. These definitions of IPD categories, subcategory codes, and descriptions will be used during the course of the study. Eligibility deviations are defined in the protocol.

The final IPD list will be used to produce the summary of IPDs table and the list of subjects with IPDs.

IPDs related to COVID-19 control measures will be summarized separately.

